7.2.3 Vital Signs

Summary statistics for vital signs will be presented at baseline, each visit, and end point. Actual values and changes from baseline to each visit and end point will be summarized using descriptive statistics. The incidence of clinically significant abnormal values will be summarized for selected vital signs using descriptive statistics.

Criteria for Clinically Significant Vital Signs

Vital Sign	Criterion value	Change relative to baseline
Heart rate	≥120 bpm	Increase of ≥15
	≤50 bpm	Decrease of ≥15
Systolic blood pressure	≥180 mm Hg	Increase of ≥20
	≤90 mm Hg	Decrease of ≥20
Diastolic blood pressure	≥105 mm Hg	Increase of ≥15
	≤50 mm Hg	Decrease of ≥15
Body temperature	≥38.3°C	Change of ≥1.1°C

In order to be identified as clinically significant abnormal, a value would need to meet both conditions: have a value beyond the criterion value and a change of at least the magnitude specified in the change from baseline column.

A listing for clinically significant abnormal vital signs will be presented.

7.2.4 Clinical Laboratory Tests

Summary statistics for biochemistry, proteinogram, hematology, and clotting laboratory tests will be presented at each visit. Actual values and changes from baseline to each visit will be summarized using descriptive statistics. All changes will be changes from the baseline value, there will be no comparisons in the values between the pre- and post FPE values. Maximal shifts from baseline during the FPE and during the LVPE will be summarized using the CTC AE grading system Version 4.03 and patient counts. Shifts for laboratory values which have no CTC AE grade will be based on the normal ranges (below, within, and above the normal range, if applicable).

	Title: Statistical Analysis Plan
	Project #: IG1002 AMBAR
	Version: Final 1.0 Effective Date: 31July2018
	Protocol Version: Version 5.0 Effective Date: Feb2018

7.2.5 Physical Examination

Physical examination results will be summarized at each visit using patient counts for each physical examination category.

7.2.6 Concomitant Medications

All concomitant medications (including prescription and over-the-counter medications) taken during the course of the study will be summarized overall. Concomitant medications for AD will be summarized separately and identified by the indication ‘Alzheimer Disease’ or any other term indicating Alzheimer Disease. Concomitant medications will be coded according to drug class using the World Health Organization (WHO) drug dictionary.

A concomitant medication is any medication that is taken at some time during IG1002 defined as:

- Medications that do not have a stop date before the first dose of study drug in IG1002, or have a start date any time on or after the first dose of study drug.

Concomitant medications will be listed for each subject according to Anatomical Therapeutic Class (ATC) Level III, preferred term and verbatim term. The World Health Organization Drug Reference List (WHODRL) will be used to classify concomitant medications by therapeutic class and preferred term. Concomitant medication usage will be summarized by the number (%) of subjects receiving each medication within each therapeutic class and preferred term. If a subject receives a particular coded medication more than once, the subject will be counted once for that coded medication. If a subject receives more than one coded medication within a therapeutic class, the subject will be counted only once in that therapeutic class.

Concomitant medication for AD will be summarized as follows on the ATC Level III and preferred drug name using counts and percentages:

- All concomitant AD medication taken at any time during the study period
- AD-Medications newly initiated during study period
- AD-Medications discontinued during study period
- AD-Medications interrupted (and re-initiated) during study period, regardless of the dose after the re-initiation
- AD-Medications with a dose increase during the study period

	Title: Statistical Analysis Plan
	Project #: IG1002 AMBAR
	Version: Final 1.0 Effective Date: 31July2018
	Protocol Version: Version 5.0 Effective Date: Feb2018

- AD-Medications with a dose reduction during the study period.

Medications missing both start and stop dates, or having a start date prior to the last dose of study medication and missing the stop date, or having a stop date after the start of study drug and missing the start date, will be counted as concomitant.

7.2.7 Overt Aggression Scale (OAS)

The OAS assesses domains: aggressive behavior of the subject and intervention of the clinician. The Total Score Aggressive Behavior ranges from 1-60, where a higher score indicates more aggressive behavior. The Total Score Intervention ranges from 0-27, where a higher score indicates more intervention. Both scores are analyzed as continuous variables, and will be summarized at each time point.

7.2.8 Agitated Behavior Scale (ABS)

The ABS comprises 14 questions that are each rated as absent (score=1), present to a slight degree (2), present to a moderate degree (3), or present to an extreme degree (4). The 14 questions are summed for a total score between 14 and 56, where a higher score indicates more agitated behavior.

The ABS is analyzed as a continuous variable, and will be summarized at each time point.

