6.1.2 Secondary Efficacy Variables

- a) Change from baseline in the cognitive, functional and neuropsychiatric scores and overall development as measured by MMSE, NPS battery, NPI, CDR-Sb, ADCS-CGIC, CSDD and C-SSRS. (6 measurements: week -3, -2 or -1 and 7-8; months 6, 9, 12 and 14) and QoL-AD, RUD-Lite[®] (5 measurements: weeks -3, -2 or -1; months 6, 9, 12 and 14). Moreover the optional questionnaires like OAS and ABS could be used at any visit in case any sign of aggression or restlessness.
- b) Variation in levels of A β ₁₋₄₀ and A β ₁₋₄₂ in CSF in the period between baseline lumbar puncture (before the start of the Intensive treatment period) and lumbar puncture immediately after the end of the last low-volume plasmapheresis (whenever this may be)
- c) Variation in the levels of A β ₁₋₄₀ and A β ₁₋₄₂ in CSF between the finalization and beginning of each of the 2 treatment periods.
- d) Levels of A β ₁₋₄₀, A β ₁₋₄₂, T-tau and P-tau in CSF throughout the study.

- e) Plasma levels of A β ₁₋₄₀ and A β ₁₋₄₂ before and after each plasma exchange for both treatment periods.
- f) Structural changes in volume of the hippocampus, posterior cingulate area, and other associated areas by MRI. Five measurements will be made (weeks -3, -2 or -1 and 7-8; months 6, 9 and 14).
- g) Variation in FDG-PET patterns (4 measurements: weeks -3, -2 or -1 and 7-8; months 9 and 14).

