6.1.3 Safety Variables

The primary criterion of safety will be the percentage of plasma exchanges (full and low-volume exchanges, including the infusion of albumin and IVIG) associated with at least one adverse event that may be related to the study procedure (adverse reactions). In addition, consideration globally will be made of the percentage plasma exchanges (full and low-volume exchanges, including the infusion of albumin and IVIG) involving some adverse event, whether or not related to the procedure.

Vital signs (blood pressure, heart rate, respiration rate, and body temperature) will be recorded before, during and after each plasma exchange session, where required. Evaluation will also be made (where required) of the different laboratory test parameters (blood cell counts, platelet count, prothrombin time (Quick), aPPT, fibrinogen, total proteins, and calcium).

During the treatment periods (before each plasma exchange) and on the days when there is no replacement, anxiety and restlessness tests will be made based on the Overt Aggression Scale (OAS) and the Agitated Behavior Scale (ABS), whenever considered opportune.

According to the criterion of the investigator, all the clinically important changes in vital function, laboratory test parameters and neuroimaging findings will be evaluated.

6.2 Conduction of the Trial. Study Procedures.

See **Appendix 8** for the **Study Summary Table** and for the **Study Flow Chart**.

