7.2 Method of Behavioral and Cognitive Testing

The established order in each visit will be as follows:

With the patient:

Rater 1

- a) MMSE (when stated by the protocol)
- b) ADAS-Cog
- c) NPS battery
 - i. RAVLT (Parts 1, 2, 3, 4 and 5)
 - ii. RAVLT (Part 6: interference)
 - iii. RAVLT (Part 6B: evocation)
 - iv. BNT (15 items)
 - v. SDMT
 - vi. Semantic and phonetic verbal fluency
 - vii. CSDD (includes the 30 minutes for differed memory)
 - viii. RAVLT (Part 7: differed memory 30 minutes after part 6B)
 - ix. RAVLT (Part 8: differed recognition)
- d) QoL-AD
- e) C-SSR (only once rater 1 has administered scales to caretaker)

Rater 2

Next, the global impairment and clinical impression scales are administered by the second evaluator:

- a) CDR-Sb
- b) ADCS-CGIC

With the care taker:

The second evaluator, while the evaluator 1 is administering the above mentioned battery, will administer the global impairment and clinical impression scale to the care taker in the following order:

- a) CDR-Sb
- b) ADCS-CGIC

The first evaluator, once he has finished the NPS battery, will interview the care taker to evaluate the subject functionality and behavior:

- NPI
- ADCS-ADL
- CSDD
- QoL-AD
- RUD-Lite

Evaluators are blinded to patient treatment. Importantly, the evaluators of the neuropsychological tests will not have access to any kind of information allowing them to identify patient assignment to treatment.

An evaluator will administer all the neuropsychological battery scales: MMSE, ADAS-Cog, NPS Battery, behavior scales NPI and CSDD and the functional scale ADCS-ADL.

The second evaluator, also on a blind basis, will administer the CDR-Sb and ADCS-CGIC. Results from previous evaluations will remain unknown for both evaluators and they must not comment any result to each other or to other study members and they will be considered blinded evaluators and will sign a document to the effect.

Anxiety and restlessness tests (during the replacement phase):

In case any sign of aggression or restlessness during the procedure, the following instruments will be used:

Measurement of overt aggression: Overt Aggression Scale (OAS)⁴⁹. This instrument measures patient aggression and provides a global score as the sum of the scores assigned to each of the different items. Increased severity is associated with higher scores.

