| Neuropsychological Tests ^A | X | | | O | O | O | O | O | O | X | O | O | O | X | O | O | X | O | O | X | O | O | X |
| Lumbar Puncture | X | | | | | | | | | X | | | | | | | | | | | | | X |
| AD Biomarkers ^B | X | | | X | X | X | X | X | X | X | X | X | X | X | X | X | X | X | X | X | X | X | X |
| Laboratory Tests ^C | X | | | X | X | X | X | X | X | X | X | X | X | X | X | X | X | X | X | X | X | X | X |
| Neuroimaging | | | | | | | | | | | | | | | | | | | | | | | |
| MRI | X | | | | | | | | | X | | | | X | | | X | | | | | | X |
| FDG-PET | X | | | | | | | | | X | | | | | | | X | | | | | | X |

FPE: Full Plasma Exchange

LVPE: Low-Volume Plasma Exchange

X: Mandatory for all groups (Treatment Group and Sham Group)

B: Before

D: During

A: After

O: ABS & OAS just if it's necessary

IV: Intermediate Visit

^A See separate breakout of Neuropsychological Tests

^B See separate breakout of AD Biomarkers

^C See separate breakout of Laboratory Tests

| Visit | Screening | | Randomi- zation | FPE 1 | FPE 2 | FPE 3 | FPE 4 | FPE 5 | FPE 6 | IV | LVP E1 | LVP E2 | LVP E3 | LVP E4 | LVP E5 | LVP E6 | LVP E7 | LVP E8 | LVP E9 | LVP E10 | LVP E11 | LVP E12 | Final | |
|---------------------------------|-----------|----|--------------------|----------|----------|----------|----------|----------|----------|-------|-----------|-----------|-----------|-----------|-----------|-----------|-----------|-----------|-----------|------------|------------|------------|-------|---|
| Time / Weeks | -3 | -2 | -1 | 1 | 2 | 3 | 4 | 5 | 6 | 7-8 | 9 | 13 | 17 | 21 | 25 | 29 | 33 | 37 | 41 | 45 | 49 | 53 | 54-55 | |
| Window Range (days) | | | | +/- 1 | +/- 1 | +/- 1 | +/- 1 | +/- 1 | +/- 1 | +/- 2 | +/- 5 | +/- 5 | +/- 5 | +/- 5 | +/- 5 | +/- 5 | +/- 5 | +/- 5 | +/- 5 | +/- 5 | +/- 5 | +/- 5 | +/- 5 | |
| Months | -1 | | | 1 | | | 2 | | | | 3 | 4 | 5 | 6 | 7 | 8 | 9 | 10 | 11 | 12 | 13 | 14 | 14 | |
| Neuropsychological Tests | | | | | | | | | | | | | | | | | | | | | | | | |
| ADAS-Cog | X | | | | | | | | | X | | | | X | | | X | | | X | | | X | |
| MMSE | X | | | | | | | | | X | | | | X | | | X | | | X | | | X | |
| NPS battery | X | | | | | | | | | X | | | | X | | | X | | | X | | | X | |
| ADCS- ADL | X | | | | | | | | | X | | | | X | | | X | | | X | | | X | |
| NPI | X | | | | | | | | | X | | | | X | | | X | | | X | | | X | |
| CDR-Sb | X | | | | | | | | | X | | | | X | | | X | | | X | | | X | |
| ADCS-CGIC | X | | | | | | | | | X | | | | X | | | X | | | X | | | X | |

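### OAS and ABS are optional and scored mainly when a patient shows agitation, but the SAP summarises them as ordinary continuous scores, so arm means describe severity among those scored, not burden in the arm

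*SAP*

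**What the plan says.** **When the scales are completed.** Protocol 6.1.2 says: "Moreover the optional questionnaires like OAS and ABS could be used at any visit in case any sign of aggression or restlessness". Protocol 7.2 ties them to the session: "In case any sign of aggression or restlessness during the procedure, the following instruments will be used". Protocol 6.1.3, which lists them under safety, is wider: "anxiety and restlessness tests will be made based on the Overt Aggression Scale (OAS) and the Agitated Behavior Scale (ABS), whenever considered opportune"; Protocol 8.3 and SAP 7.2 repeat this. In Appendix 8 the legend reads "O: ABS & OAS just if it's necessary", and both scales carry the optional mark at every visit, including screening. No section makes either scale routine.

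**How they are analysed.** SAP 7.2.8 says of the ABS: "The ABS is analyzed as a continuous variable, and will be summarized at each time point". SAP 7.2.7 says of the two OAS totals: "Both scores are analyzed as continuous variables, and will be summarized at each time point". SAP section 7 applies its general rules to both scales: summaries of the actual value and of change from baseline, an extra summary of the last post-baseline value for safety variables, and no filling in of missing scores. The output for a continuous variable is the count, mean, standard deviation, standard error, median, minimum and maximum. SAP 7.2 presents safety results by treatment group.

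For these two scales the SAP plans no percentage of patients or sessions assessed, and gives no rule for reading a scale that was not completed.

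**The concern.** Whether a score exists depends largely on the behaviour that the score measures. A patient who stays calm will usually have no record rather than a low score. A mean over available scores is then conditional on having been selected for scoring. Adding many mildly restless patients to an arm pulls its mean down, even though the arm now has more agitation. Change from baseline is weaker still: the baseline score is optional too, so a change exists only for patients scored at both visits.

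Both scales are listed among the safety variables, and the protocol names anxiety as a possible adverse effect of the exchange procedure (5.2.2 and 5.2.2.6). A reader comparing arms on the planned means could draw the wrong conclusion about how the sessions are tolerated.

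**Working it through.** The documents state no expected rate or score for either scale, so there is no figure to reproduce. The check asks how the planned mean behaves when scoring is triggered.

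**Inputs from the documents.** 364 subjects randomised 1:1:1:1 gives 364/4 = 91 per arm (Protocol 4.3 and 3.2). The ABS floor comes from SAP 7.2.8: "The 14 questions are summed for a total score between 14 and 56, where a higher score indicates more agitated behavior", with 14 meaning that every item is absent.

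**Assumed inputs.** In sham, 5 patients are scored, all at ABS 32. In active, the same 5 at 32 are joined by 5, 10 or 15 mildly agitated patients at 20. For the all-patient mean only, an unscored patient counts as 14.

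**Formulas.**
- Planned mean = sum of scores / number scored.
- Share scored = number scored / 91.
- All-patient mean = (sum of scores + 14 × number unscored) / 91.

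| Arm | Scored | Planned mean | Share scored | All-patient mean |
|---|---|---|---|---|
| Sham | 5 | 160/5 = 32.0 | 5/91 = 5.5% | (160 + 86×14)/91 = 14.99 |
| Active, 5 mild | 10 | 260/10 = 26.0 | 10/91 = 11.0% | (260 + 81×14)/91 = 15.32 |
| Active, 10 mild | 15 | 360/15 = 24.0 | 15/91 = 16.5% | (360 + 76×14)/91 = 15.65 |
| Active, 15 mild | 20 | 460/20 = 23.0 | 20/91 = 22.0% | (460 + 71×14)/91 = 15.98 |

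As agitation spreads in the active arm, the planned mean moves away from sham in the favourable direction. The other two measures move the opposite way.

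**A case without reversal.** Suppose severity is normal with mean μ and SD 1, a patient is scored when severity exceeds 0, and treatment shifts everyone upward. The share scored is Φ(μ), and the mean among those scored is μ + φ(μ)/Φ(μ).
- μ = −1.64: share 5.1%, mean 0.42 SD above the threshold.
- μ = −1.0: share 15.9%, mean 0.53 SD.
- μ = −0.5: share 30.9%, mean 0.64 SD.

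From the first to the last case the share rises about sixfold (30.9/5.1 = 6.1), while the scored-only mean rises by a factor of 1.5 (0.64/0.42). The direction is right, but most of the difference is missed.

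**The case against.** Five points can be made for the plan.

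1. A reader might infer that the frequency of scoring goes unreported. It does not: the count is part of every continuous summary, by arm and time point, so 20 against 5 would be visible beside the means. What is missing is the percentage and its denominator. This stands as a limit on the point.
2. A reader might infer that only agitated patients are ever scored. Protocol 6.1.2 and 7.2 read that way, but 6.1.3, 6.2.2, 6.2.4 and Appendix 8 leave it to discretion or need, so a calm patient may be scored. This stands: the selection is strong but not absolute.
3. Agitation is recorded elsewhere. The NPI covers aggression, restlessness, irritability and anxiety, and is mandatory at baseline, weeks 7-8 and months 6, 9, 12 and 14. Adverse events are tabulated by term, and the percentage of exchanges with an event is planned (SAP 7.2.1 and 7.2.2). The cover is partial. The NPI is not scheduled at the six full-exchange visits and is reported as two totals (SAP 7.1.5), and Protocol 9.1.1 excludes incidents clearly due to progression from adverse events.
4. Reversal depends on inputs chosen to produce it. This is correct, and the second calculation shows a plausible case without it.
5. A completion rate is not a clean measure either. Protocol 3.4 lists patients, caregivers and raters as blind, not the staff who run sessions, so the decision to score may differ by arm. Version 1.0 controls had no sham treatment but are pooled into the control arm (SAP 2.1). Both facts stand, and the fix must deal with them.

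**Conclusion.** The point holds as one about descriptive safety reporting. The planned OAS and ABS means estimate severity among those scored; they do not estimate burden in the arm. They can understate a difference between arms and, when the extra cases are milder than the existing ones, can reverse it. In the illustration the planned means are 32.0 (sham) and 23.0 (active), against shares scored of 5.5% and 22.0%.

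Those sizes rest wholly on assumed counts and scores. The all-patient means also assume that every unscored patient would score 14, which no section states; the shares scored need no such assumption.

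A reader might infer that the active arms will look calmer than they are, or that the trial's findings are compromised. The documents support neither. They give no agitation rates from which to predict a direction. SAP 9.2.3 makes all safety analyses descriptive, the primary safety criterion is the percentage of exchanges with a related adverse event (SAP 7.2), and no efficacy conclusion depends on these scales.

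**What to change.** In SAP 7.2.7 and 7.2.8:

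- Report, by arm and by phase (intensive, maintenance), the number and percentage of safety-set patients with at least one completed OAS or ABS, and the number and percentage of performed sessions, real or sham, with one completed. Count each session once.
- Show scores descriptively among those assessed only, labelled as conditional on assessment, with the count.
- Drop change from baseline for both scales.
- Leave Version 1.0 controls out of the session-based rates, because they had no sham sessions, and footnote their presence in the patient-based rates.
- State that completion was at the discretion of staff who are not listed as blinded, so the rates are themselves open to ascertainment bias.

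The cost is SAP wording and one table from data already collected, provided that performed sham sessions are recorded so that they can serve as a denominator. The SAP already reports percentages of exchanges (7.2.1) and incidence of abnormal vital signs (7.2.3), so the format is not new.

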7.3 OTHER END POINTS

7.3.1 Biomarkers

Levels of $A\beta_{1-40}$, $A\beta_{1-42}$, T-tau, and P-tau, in cerebral spinal fluid will be collected at the randomization visit, the intermediate visit, and at the final visit. Actual values and changes from baseline at each point in time and at end point will be summarized. Furthermore, the change from the intermediate visit until the final visit will be summarized.

$A\beta_{1-40}$, $A\beta_{1-42}$ will be analyzed before and after each plasma exchange. Absolute values and the changes from baseline will be summarized separately for the values before the plasma exchange and after the plasma exchange. The change in the plasma levels (after plasma exchange – before plasma exchange) will be summarized also.

	Title: Statistical Analysis Plan
	Project #: IG1002 AMBAR
	Version: Final 1.0 Effective Date: 31July2018
	Protocol Version: Version 5.0 Effective Date: Feb2018

All other biomarkers (β -secretase, γ -secretase, cholesterol, LDL, HDL, VLDL, CRP, rheumatoid factor, IL-1b, IL-6, ferritin, TNF- α , RBC, WBC, lymphocytes, monocytes, neutrophils, eosinophils, glucose, proteins, and albumin) will be analyzed descriptively (absolute values and changes from baseline) as deemed appropriate.

All biomarker data will be analyzed as continuous variables. If the assumption of normality of the changes from baseline is significantly violated (Shapiro-Wilk test <0.05), changes in the biomarkers will be compared between the treatment groups by a Kruskal-Wallis Test. Statistical comparisons for the changes in $A\beta_{1-40}$, $A\beta_{1-42}$ in plasma will only be performed for the values before and after the plasma exchange. Further exploratory analyses, e.g. correlation between the biomarkers and the cognitive, functional, and neuropsychiatric scores, can be performed as deemed appropriate.

7.3.2 Magnetic Resonance Imaging (MRI)

Magnetic resonance imaging data will be analyzed by MMD. The analysis will be specified in a separate SAP document.

7.3.3 Functional Brain Changes through FDG-PET

Functional brain changes through FDG-PET data will be analyzed by MMD. The analysis will be specified in a separate SAP document.

There are no other end points (e.g., PK, PD, Outcomes Research) in the study.

7.4 COVARIATES

For the analysis of the cognitive, functional, and neuropsychiatric scores, the corresponding baseline scores, age, and AD severity will be used as a covariate for each change from baseline model. Disease severity will be defined by the baseline MMSE score as follows:

- MMSE 18 – 21 points
- MMSE 22 – 26 points

An exception is the model for the changes from baseline for the MMSE. This model will only be adjusted for age and the baseline value. Also the models for the subgroups by severity will only be adjusted for age and baseline value.

